11.2 Sample size

The sample size in the literature varies. The planned number of 24 subjects is within the wide range and is expedient, time-wise and financially feasible for the study.

The G*Power analysis (V.3.1.) revealed (F-test, MANOVA:repeated measures, within-between interaction, effect size $f(V) = 0.9$, alpha err prob = 0.05, Power (1-beta err prob) = 0.6, number of groups = 3, number of measurements = 14) a required group of 23 participants.

11.3 Criteria for the statistical use of data in the case of incomplete data sets

Only data from subjects who have completed the entire protocol will be included in the study. This ensures that all data has been collected under the same conditions and thus remains homogeneous and comparable.

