--	--

SUPSI

Measurements and procedures:	
Lactate and creatine kinase
 
The lactate and creatine kinase measurement are carried out by capillary blood measurement (Accutrend, Roche Diagnostic, Rotkreuz, Switzerland & Reflotron, Roche Diagnostic, Rotkreuz, Switzerland). This measurement is measured during the baseline measurements, after the step-up task and up to 30 min after the cold water bath of the hand (5 min interval).
 
Balance measurement
 
The fluctuations of the hull are recorded and evaluated with the Sway Star™ System (www.b2i.info). The Sway Star™ is a measuring instrument that contains gyroscopes. It is attached to a belt that is placed around the patient's waist. The data is evaluated with the associated Sway Star™ software and transferred to the data sheet. This measurement is carried out after the baseline measurement and after the cold water bath immersion of the hand.
 
Pain sensation
 
The pain threshold is measured using a pain pressure algometer (NOD, www.to-nod.com). This measurement is carried out after the baseline measurement and after the cold water bath immersion of the hand.
 
Psychological measurements
 
The psychological measurements (sleep disorder, altitude sickness, dyspnea, state of mind, drowsiness) are evaluated on the basis of written questionnaires.
 
The cognitive test battery consists of 8 tasks (ANAM, US Department of Defence, Vista Life Sciences, USA), which are carried out on a laptop computer.
 
These measurements are carried out after the baseline measurement and after the cold water bath immersion of the hand.
 
Thermal comfort and temperature perception
 
These parameters are measured using a scale. This measurement is carried out after the baseline measurement and after the cold water bath immersion of the hand .
 
Further processing of the data
 
Windows uses Excel for data pooling and the graphical representation of the end data® .

Study Product / Intervention:	Cloud 9
Control Intervention (if applicable):	As a control, the subjects are observed under normobaric and normoxic conditions.
Number of Participants with Rationale:	We limit the number of subjects to n = 24 study participants due to the available financial resources and due to the power analysis carried out.

Study Duration:	June 2019-December 2020
------------------------	-------------------------

SUPSI

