3.6 Peers

The intervention group is also the control group, as a crossover design is used.

Randomization

Randomization takes place according to the situation (normobar & normoxic vs. normobar & hypoxic). The situation you find yourself in first is decided by drawing lots.

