11.4.2 Primary Analysis

The statistical data analysis will be carried out by [name]. [name] after completion of the data collection of the entire project.

Repeated measures analysis of variance (MANOVA)

2 factors:

Factor 1: Situation (simulated altitude vs. terrestrial altitude)

Factor 2: Time (baseline, after step-up task, 0, 5, 10, 15, 20, 25, 30 min post-cold water immersion of the hand)

Repeated measures analysis of variance (MANOVA)

2 factors:

Factor 1: Situation (simulated altitude vs. terrestrial altitude)

Factor 2: Time (baseline, post-cold water immersion of the hand)

The significance level is set at $P < 0.05$, and the statistical data analysis is carried out with SPSS V. 23.

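### The sample-size calculation in section 11.2 models three separate groups measured 14 times, so its 23 participants at 60% power describe neither of the planned within-subject analyses

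*Combined protocol and SAP*

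**What the plan says.** Section 11.2 gives two reasons for 24 participants: the number lies within the range seen in the literature and is feasible, and a G*Power calculation was run. The option entered was "F-test, MANOVA:repeated measures, within-between interaction", with f(V) = 0.9, "alpha err prob = 0.05", "Power (1-beta err prob) = 0.6" and "number of groups = 3, number of measurements = 14) a required group of 23 participants". The synopsis, under the number of participants, rests the sample size on this calculation as well as on money: "due to the available financial resources and due to the power analysis carried out".

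The design is described elsewhere. Section 3.6: "The intervention group is also the control group, as a crossover design is used". Section 9.2.2 (conclusion and compensation) ends a participant's involvement only once every situation has been completed. Section 11.4.2 plans a two-factor repeated-measures analysis. Factor 1 is situation, simulated versus terrestrial altitude. For the first set of outcomes the second factor is "Factor 2: Time (baseline, after step-up task, 0, 5, 10, 15, 20, 25, 30 min post-cold water immersion of the hand", which is nine levels. For the other set it is baseline and after immersion, which is two levels.

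**The concern.** A within-between interaction needs a between-subject factor, that is, different people in each group. With three groups and N=23, the software assumes about eight people per group. In this trial the same people supply the data for every situation, so the situation comparison is made within each person. The normobaric normoxic control is not a level of the analysed factor, and the number of measurements entered matches neither time factor.

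At stake is the only quantitative support for N. A reader of section 11.2 cannot tell what simulated-versus-terrestrial difference 24 people can detect. The effect size has no source, and a target power of 0.6 accepts a 40% chance of missing even that effect.

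**Working it through.** **Step 1. Reproduce the stated 23.** Inputs from section 11.2: k = 3 groups, m = 14 measurements, f(V) = 0.9, alpha 0.05, target power 0.60. For the Pillai trace:

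- s = min(k−1, m−1) = min(2, 13) = 2
- df1 = (k−1)(m−1) = 2 × 13 = 26
- df2 = s(N−k−(m−1)+s); at N=23, 2 × (23−3−13+2) = 18
- λ = N·s·f² = 23 × 2 × 0.81 = 37.26
- critical F(26, 18) = 2.134; power = 0.647
- at N=22: df2 = 16, λ = 35.64, power = 0.586

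So 23 is the smallest total N that reaches 0.60. The choice of λ is inferred from this match: λ = df2·f² would give 31, and λ = N·f² would give 32.

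**Step 2. Compare the model with the trial.**

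| Feature | Section 11.2 calculation | Trial (sections 3.6, 9.2.2, 11.4.2) |
|---|---|---|
| Situation | between-subject, 3 groups | within-subject, 2 analysed levels |
| Repeated measurements | 14 | 9 or 2 time points |
| Tested effect | group × time, df1 = 26 | situation × time, (2−1)(9−1) = 8 df or (2−1)(2−1) = 1 df |

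Products of the design do not give 14 either: 2 × 9 = 18 and 3 × 9 = 27.

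**Step 3. Can the stated inputs be carried over?** Not cleanly. With V = s·f²/(1+f²), f(V) = 0.9 means V = 2 × 0.81/1.81 = 0.895 when s = 2, but 0.81/1.81 = 0.448 when s = 1. If f = 0.9 is kept nominally as an assumption, power at N=24 for the 2 × 9 within-subject test is 71.0% with λ = N·f², or 50.3% with λ = df2·f². For the 2 × 2 test it is 98.8%. No single power figure covers both analyses.

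**Step 4. Sensitivity of the planned tests.** This needs no outside effect size. Use a one-sample Hotelling T² on the q within-person situation × time contrasts: F on (q, N−q) df with λ = N·D², where D is the Mahalanobis distance. For q = 1, D is the standardised paired difference (mean of the individual contrast divided by its SD), and the test is a two-sided paired t test. One outcome, alpha 0.05, no multiplicity adjustment:

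| N | Test | Critical F | D for 80% power | D for 60% power |
|---|---|---|---|---|
| 24 | 8 df (2 × 9) | 2.591 | 0.99 | 0.81 |
| 24 | 1 df (2 × 2, or one paired contrast) | 4.279 | 0.60 | 0.47 |

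Check for 1 df at 80%: λ = 24 × 0.597² = 8.56.

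**Step 5. Two illustrations, both resting on assumptions of this review.**

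- If 20 participants complete (the documents give no dropout rate), D for 80% power becomes 0.66 for 1 df and 1.15 for 8 df.
- Section 11.1 has 14 primary hypothesis blocks: eight physiological, including balance and pain, and six psychological. With Bonferroni, alpha = 0.05/14 = 0.00357, and the 1-df figure at N=24 rises from 0.60 to about 0.85. At that alpha, power for a difference of 0.60 is about 40%.

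**The case against.** The sponsor can fairly say that the software output is correct, that section 11.2 already calls 24 expedient and feasible, that the synopsis names finances first, and that a power of 0.6 is openly disclosed for a basic-science study in healthy volunteers. All of that stands. Low power is a comment on the plan, not an error in it, and the fault here is the choice of model, not a slip in calculation.

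It can also be said that the trial does have a between-subject factor. Order, normoxic or hypoxic first, is drawn by lot (sections 3.6 and 7.3), so sequence has two levels. That is right as far as it goes, but sequence is not in the planned analysis and does not supply three groups. The 3 may well stand for the three situations, which are within-subject.

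A third objection concerns any replacement figure. Section 11.4.2 names no single outcome, time point or summary as the primary contrast, and terrestrial altitude is measured both on arrival and the next day (sections 8.2.1 and 9.2.2). To quote only the 1-df figure of 0.60 would give the favourable number for a contrast that the plan does not define. This stands, and it is why the 8-df figure and the multiplicity caveat must appear beside it.

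A reader might also infer that the 14 came from counting the hypothesis blocks in section 11.1. The counts agree, but the documents do not say where the input came from.

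**Conclusion.** The concern holds as a mismatch between design and model. The 23 participants at 60% power are correct output for a trial with three separate groups and 14 measurements, and they describe neither the 2 × 9 nor the 2 × 2 within-subject analysis. The synopsis should not cite the calculation as a reason for N. It should be fixed, but it changes neither N, nor the analysis, nor what participants undergo.

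Two stronger readings are tempting and are not supported:

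- **That 24 is too few.** The documents give no sourced effect size for the within-subject contrast. At the same nominal f = 0.9, the 2 × 9 test would need 22 people for 60% power under one noncentrality convention and 27 under the other, so the mismatch does not point in one direction.
- **That a null result could not be interpreted.** Confidence intervals show which differences remain compatible with the data, whatever planning calculation was used.

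The sensitivity figures (0.99 for 8 df and 0.60 for 1 df at 80% power) assume 24 complete participants, approximately normal within-person contrasts, one outcome, and two-sided 0.05 without adjustment.

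**What to change.** Keep N = 24. In section 11.2 delete the G*Power sentence, and in the synopsis delete the reference to the power analysis. Replacement text could read:

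> The sample size of 24 is set by feasibility. For a single outcome at two-sided alpha 0.05, unadjusted for multiplicity, 24 complete participants give the 2 × 9 situation-by-time test (8 df) 80% power for a Mahalanobis distance of 0.99 (60% for 0.81). They give the 2 × 2 interaction, or any one-degree-of-freedom paired contrast of simulated versus terrestrial altitude, 80% power for a standardised paired difference of 0.60 (60% for 0.47). These figures do not hold jointly over all primary outcomes; with Bonferroni over 14 hypotheses the 1-df figure would be about 0.85.

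State which terrestrial measurement, arrival day or next day, enters the contrast. If a completer scenario is added, label it as an assumption (for example 20 completers: 0.66 for 1 df, 1.15 for 8 df).

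The cost is one paragraph, one synopsis line and a decision on the terrestrial day, with no extra participants. The sponsor gives up the claim that a power analysis produced 23.

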11.4 Scheduled analyses

11.4.1 Datasets and Data Population

Only datasets that can be used sensibly will be included in the study. Incomplete data sets that contain only part of the protocol are included in the analysis as far as possible. No new test subject is being sought to replace the missing data.

SUPSI

11.4.2 Primary Analysis

The statistical data analysis will be carried out by [name]. [name] after completion of the data collection of the entire project.

Repeated measures analysis of variance (MANOVA)

2 factors:

Factor 1: Situation (simulated altitude vs. terrestrial altitude)

Factor 2: Time (baseline, after step-up task, 0, 5, 10, 15, 20, 25, 30 min post-cold water immersion of the hand)

Repeated measures analysis of variance (MANOVA)

2 factors:

Factor 1: Situation (simulated altitude vs. terrestrial altitude)

Factor 2: Time (baseline, post-cold water immersion of the hand)

The significance level is set at $P < 0.05$, and the statistical data analysis is carried out with SPSS V. 23.

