7.3 Allocation of situations

The situation assignment (normobar & normoxic vs. normobar & hypoxic) is done concealed by means of a lot in a sealed envelope, which is drawn under the supervision of the study leader. This lot shows whether the subject first goes through the normobaric & normoxic situation or the normobar & hypoxic situation.

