- H0 The quality of sleep does not change significantly at the simulated altitude compared to the terrestrial altitude.

- H1 The quality of sleep changes significantly in the simulated altitude compared to the terrestrial altitude.

Symptoms of altitude sickness

- H0 The simulated altitude does not lead to any symptoms of altitude sickness compared to the terrestrial altitude.

- H1 The simulated altitude leads to symptoms of altitude sickness compared to the terrestrial altitude.

Dyspnea

- H0 The simulated altitude does not lead to dyspnea symptoms compared to the terrestrial altitude.

- H1 The simulated altitude leads to dyspnea symptoms compared to the terrestrial altitude.

State of mind

- H0 The simulated altitude does not lead to any changes in mood compared to the terrestrial altitude.

- H1 The simulated altitude leads to changes in state of mind compared to the terrestrial altitude.

Sleepiness

- H0 The simulated altitude does not lead to any drowsiness symptoms compared to the terrestrial altitude.

- H1 The simulated altitude leads to drowsiness symptoms compared to the terrestrial altitude.

Cognition

- H0 The simulated altitude does not lead to any cognitive changes compared to the terrestrial altitude.

SUPSI

- H1 The simulated altitude leads to cognitive changes compared to the terrestrial altitude.

Thermal comfort and temperature perception

- H0 The thermal comfort and the temperature perception do not change significantly in the simulated altitude compared to the terrestrial altitude.
- H1 Thermal comfort and temperature perception change significantly in the simulated altitude compared to the terrestrial altitude.

A 2-factor analysis is carried out.

Factor 1: Situation (simulated altitude vs. terrestrial altitude)

Factor 2: Time (baseline, after step-up task, 0, 5, 10, 15, 20, 25, 30 min post-cold water immersion of the hand) or

Time (baseline, post-cold water immersion of the hand)

Explanations for the hypotheses:

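### The drawn order of the two laboratory sessions is absent from the primary model, which costs some precision on the Situation effect; adding it recovers that precision but not the bias from an unrandomised terrestrial session

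*Combined protocol and SAP*

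**What the plan says.** Section 7.3 describes the allocation: "This lot shows whether the subject first goes through the normobaric & normoxic situation or the normobar & hypoxic situation". Sections 3.6 and 6.1.1 say the same. Terrestrial altitude is not part of the draw.

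Section 11.1 announces the model: "A 2-factor analysis is carried out". Section 11.4.2 sets it out as two repeated-measures analyses. Each has "Factor 1: Situation (simulated altitude vs. terrestrial altitude" as its first factor and Time as its second, with nine levels for most physiological measures and two levels for the rest. The synopsis gives the same two factors. Order, sequence and period appear in none of these places, and section 11.4.3 says there is no secondary analysis that could take them up.

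Section 11.2 plans the trial with "alpha err prob = 0.05" and "Power (1-beta err prob) = 0.6". It finds 23 participants necessary and sets 24.

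**The concern.** Simulated altitude is the first laboratory session for some participants and the second for the others. Several outcomes could change with repetition alone. The eight-task cognitive battery is taken twice in each of four measurement sessions. The pressure-pain threshold, the step-up task and the cold-water bath are also repeated. Such a change shifts a participant's simulated values by an amount that depends on the drawn order.

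The order is known and was randomised, so the model could account for this shift. As written, it counts the shift as unexplained variation between people in the simulated-minus-terrestrial difference. Intervals for the Situation effect then become wider than they need to be, in a trial whose planned power is only 60%.

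**Working it through.** **The plan's own figure.** Inputs from section 11.2: f(V) = 0.9, alpha 0.05, power 0.6, and "number of groups = 3, number of measurements = 14". For a multivariate within-between interaction, take p = 14 - 1 = 13, q = 3 - 1 = 2 and s = 2. Then df1 = 26, df2 = 2(N - 3 - 13 + 2) and noncentrality = N x 2 x 0.81.
- N = 22: df2 = 16, noncentrality 35.64, power 0.586.
- N = 23: df2 = 18, noncentrality 37.26, power 0.647.

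So N = 23 is reproduced. This calculation concerns a three-group interaction, not the Situation contrast of 11.4.2. Below, 60% serves only as a benchmark.

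**Set-up.** Let pi1 and pi2 be the session effects of the first and second laboratory sessions and piT that of the terrestrial session. Let delta = pi2 - pi1, in units of the within-order SD of the paired difference d = simulated minus terrestrial. Let theta be the true difference. Assume N = 24 with 12 per order.
- Simulated first: mean of d = theta + pi1 - piT.
- Simulated second: mean of d = theta + pi2 - piT.
- Average over the two orders: theta + (pi1 + pi2)/2 - piT.
- Each order lies delta/2 from that average, on opposite sides.

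A session effect therefore has two parts. The between-order part, plus or minus delta/2, goes into the error term if order is omitted. The mean part, (pi1 + pi2)/2 - piT, goes into the Situation contrast whether or not order is modelled.

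**The between-order part.** Without order, the expected variance of d is 1 + (delta^2/4)(24/23). At delta = 0.5 this is 1 + 0.0625 x 1.0435 = 1.065. With order in the model (22 error df), an effect of 0.473 SD has 60% power in a two-sided 5% test. Simulating the test without order (23 df), with the mean part set to zero, gives:

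| delta | Variance ratio | Power without order | Power with order | Type I error without order |
|---|---|---|---|---|
| 0.5 | 1.07 | 0.58 | 0.60 | 4.3% |
| 0.75 | 1.15 | 0.55 | 0.60 | 3.7% |
| 1.0 | 1.26 | 0.51 | 0.60 | 2.9% |

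The loss is about 2, 5 and 9 points.

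**The mean part.** Suppose the terrestrial session comes last and the change levels off after the first session, so piT = pi2. The contrast is then biased by -delta/2. With no true difference, the type I error is:

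| delta | Without order | With order |
|---|---|---|
| 0.5 | 20% | 22% |
| 1.0 | 56% | 65% |

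The order term does not touch the bias. The rejection rate rises slightly because the standard error is smaller. If instead the terrestrial session fell between the two laboratory sessions, with a linear drift of 0.5 SD per session, the mean part would be zero. Delta would then be 1.0 and the type I error without order 2.9%.

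**Situation x Time.** A session shift that is the same at every time point cancels from this interaction, so the losses above apply to the Situation main effect only.

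**Cost of the term if delta = 0.**
- Main effect: 23 against 22 error df gives power 0.602 by the noncentral t (0.603 by simulation) against 0.600, or 0.2 to 0.3 points.
- Nine-level multivariate Situation x Time test: 8 contrasts, and error df falls from 24 - 8 = 16 to 15. A noncentrality giving 60% power at 16 df gives 58.7% at 15, or about 1.3 points.

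**The case against.** A reader might infer from the table that every session effect ends up in the error term, so that the planned tests are conservative and their true type I error is below 5%. The documents do not support this. It requires the terrestrial session's own effect to lie near the average of the two laboratory sessions. That session is outside the lot, and its position is not clearly stated. Section 9.2.2 (step 2.3) is garbled but suggests that it follows the laboratory work. Practice and habituation usually build up or level off, so a return to the midpoint at a later session is not the natural expectation. Under a plateau the test is anti-conservative. This part of the objection stands in full.

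A reader might also take order to be the only thing randomised. Section 9.1.2 mentions a measurement side that depends on randomisation, so that reading is too strong.

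It is also fair to object that delta is unknown and that the loss is only about 2 points at 0.5 SD. Repetition effects are plausible for cognition, pain and the physical tasks, but less obviously so for saturation, perfusion, lactate or creatine kinase. The 12/12 split is assumed, since the protocol specifies only a lottery. These points limit the size of the concern. They do not remove it: the between-order part is left in the error term wherever the terrestrial session falls, and the label that would take it out is already recorded.

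**Conclusion.** The point holds as a modest loss of precision. Leaving the drawn order out of the model inflates the variance of the simulated-minus-terrestrial difference by about 7%, 15% and 26% at delta = 0.5, 0.75 and 1.0 SD. On the Situation main effect this costs about 2, 5 and 9 points of power against a 60% benchmark.

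These figures rest on an assumed delta, on 12 participants per order, and on a session shift that is constant over time points. The power figures also take the mean part of the session effect as zero. Nothing here shows the overall test to be conservative. Bias from the unrandomised position of the terrestrial session is a separate and potentially larger problem, which an order term neither causes nor cures.

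**What to change.** In section 11.4.2, add Order (control first or simulated first, as drawn under 7.3) as a between-subject factor with its interactions in both repeated-measures models. The Order x Situation interaction is the term that takes up the between-order shift, so it must be kept. Test Situation and Situation x Time averaged over the two orders with equal weight. Make the same change in section 11.1 and in the synopsis. State that the term recovers precision only and does not correct for where the terrestrial session falls.

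The change uses the recorded lot and the SPSS procedure already planned, with no new data. It uses one error degree of freedom, at the cost in power shown above if there is no order effect.
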